3. **Research Plan:** Summarize the study design and research procedures using non-technical language that can be readily understood by someone outside the discipline. **Be sure to distinguish between standard of care vs. research procedures when applicable, and include any flowcharts of visits specifying their individual times and lengths.** Describe the setting in which the research will take place.

1. Study Design and Overview

Ninety treatment seeking men and women with AUD will be recruited to participate in and complete this preliminary study. Participants will be recruited through flyers and advertisements in local newspapers and from community substance abuse treatment facilities. Subjects will participate in an initial screening and intake session to obtain informed consent, followed by physical examination and blood work to determine eligibility. Eligible

participants will be randomly assigned to 2 doses of PREG (300/500 mg/day) vs placebo (PLA) treatment (N=30/group) over 8 weeks. In week 2, AUD patients will participate in a 3day human laboratory study where they will be exposed to three experimental sessions of stress, alcohol cue and neutral-relaxing imagery on separate days (Fox et al.,2007; 2009; Sinha et al., 2008; 2009; 2011). Throughout the study, participants will come twice-weekly to the Yale Stress Center to receive medication, counseling and provide urine samples for UTOX. Women will be enrolled during the mid-luteal phase of the menstrual cycle so that laboratory sessions will be scheduled during the early to mid-follicular phase of the cycle when endogenous sex hormone levels are low prior to ovulation. PREG doses and matching placebo will be obtained by Yale IDS for compounding and dosing to 300mg and 500mg of PREG or PLA. Participants will self-administer study medication on a twice-daily dosing schedule throughout entire study.

Subjects will begin with full respective dose of medication immediately without a titration period, as previous studies with similar doses of pregnenolone up to 500 mg/day at b.i.d. dosing to be well tolerated and with no side effects (Marx et. al., 2009; Marx et al., 2014; Brown et al., 2014; Sripada et al., 2013).

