Once a subject is deemed eligible, signs consent and completes all intake assessments, s/he will be randomized to 300mg PREG, 500mg PREG, or PLA and exposed to three laboratory sessions as close together as possible of guided imagery of stress, drug cues and neutral-relaxing cues in week 2 (identified as lab DAY 1, DAY 2, and DAY 3). In a session prior to laboratory sessions, subjects will participate in an imagery script development to provide descriptions of recent stressful, drug cue related and neutral relaxing situations to the research assistant. On the day before laboratory session 1 , subjects will participate in a relaxation and imagery training and IV habituation session, followed by three laboratory sessions that include IV blood drawing.

Daily surveys using a Smartphone platform (MetricWire) monitoring will prompt subjects to take study medication, and provide responses on their alcohol use, craving, stress and mood states for the day (see below for detailed description).

Genetic studies:

Ten mL of whole blood will be collected during physical examination to assess eligibility, and thirty-two mL of whole blood will be also collected from patients on the day of the first laboratory session (LAB DAY 1) for the purposes of understanding genetic factors that may affect craving.

Throughout the 8 week study, subjects will self-administer 300mg/day, 500mg/day or PLA/day and study staff will provide weekly medication packs to subjects.

Participants will be seen twice per week at the Yale Stress Center at [name] to receive once/week counseling, provide urine and receive contingency management for treatment attendance. Daily surveys using the smartphone platform (MetricWire) monitoring will prompt subjects to take study medication, and provide responses on their alcohol use, craving, stress and mood states for the day. Smartphone data will be collected daily. Subjects will be prompted at two random times in the morning and afternoon to complete a brief 1-minute survey of questions and a third 5-10 minute survey to be completed at night before bedtime. The surveys are set up with standard automated questions and prompts and subjects will use the smartphone key pad to answer the prompts (via MetricWire).

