Contact and collateral information will have been obtained from subjects at intake. We currently use procedures that make it possible to locate and re-interview more than 90% of the patients recruited into our treatment and laboratory research studies. Of note, in our past completed stress studies with alcohol dependent individuals we obtained a 92% completion rate. Our procedures include informing the patient of the importance of follow-up evaluations at the time of initial assessment, emphasizing the patient's role as a research subject, guaranteeing complete confidentiality of all information, obtaining permission, addresses and telephone numbers of three collaterals to be contacted in order to help us locate the subject, arranging for home visits and telephone interviews when subjects fail to keep appointments, mailing of appointment reminders that are followed by telephone calls, and provision of incentive payments for successful completion of follow-up evaluations. All of these procedures will be incorporated into this study.

Laboratory Sessions:

Rationale for Use of Personalized Imagery Procedures. Emotional imagery paradigms have been widely used in behavioral research studies examining the pathophysiology of anxiety disorders, including panic disorder, obsessive compulsive disorder and PTSD (Cook, Melamed, Cuthbert, McNeil, & Lang, 1988; Foa & Kozak, 1986; McNeil, Vrana, Melamed, Cuthbert, & Lang, 1993; Pitman, Orr, Forgue, de Jong, & Claiborn, 1987; Shalev, Orr, & Pitman, 1993; Orr et al., 1998; Orr, Pitman, Lasko, & Herz, 1993). These procedures are known to activate the same physiological, subjective and behavioral components as the emotion trigger situations, thus being a useful clinical research procedure for inducing stress/emotional states. Similar imagery induction procedures have been successfully adapted by our group in previous studies to induce specific emotion states in normal volunteers and stress and drug cues in alcohol dependent individuals (Sinha, Lovallo, & Parsons, 1992; Sinha & Parsons, 1996; Sinha, Catapano, & O'Malley, 1999a;).

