Laboratory Sessions. In week 2 of the study PREG/PLA administration and hence DAY 1, 2 and 3 of the laboratory portion of the study, subjects will be brought into the research testing rooms of the Yale Stress Center (YSC) at 2:00 PM. The laboratory sessions will only be conducted if the subject has a breath alcohol level of 0, otherwise the session will be rescheduled. The subject will then be prepared for physiological assessments. An indwelling intravenous (IV) catheter will be inserted by the research nurse specialist in the antecubital region of the subject's non-preferred arm for blood sampling. Blood samples will be obtained periodically for assessment of neuroactive steroids, ACTH, cortisol, prolactin, NE and EPI levels. A blood pressure cuff will be placed on the subject's preferred arm to monitor blood pressure (BP) periodically. On-line assessment of physiological measures will be obtained at specified time periods during the laboratory sessions. Self-reports of emotional state, anxiety and alcohol craving will also be assessed periodically.

After preparation of assessments and a 40 minute adaptation period, two blood draws before imagery will be conducted (BASELINE). After the second blood draw, a 5-minute baseline period will follow to assess continuous pulse rate and BP assessments. Following the baseline period, instructions for conducting imagery will be provided. The order and content of the imagery condition will not be revealed to the subject or to the research staff conducting the

sessions. In the imagery task the subjects will be asked to imagine the situation being described vividly, 'as if it were happening right now", until asked to stop. The imagery script will be played to the subject over headphones and the subject will be required to imagine the situation for 5 minutes. A tape recording for each subject's script will be developed prior to the testing situation and recorded by the same person for each subject. Immediately following imagery, a blood draw will be conducted (IMAGERY). Thereafter, four recovery blood draws will be conducted at 15 minute intervals (RECOVERY). Timeline for assessments is detailed in Table 1.

TABLE 1: Schedule for Laboratory Sessions

LAB DAY 1 11AM: Imagery and Relaxation Training and IV Habituation session (1 hour)

LAB DAY 1, 2 and 3: LABORATORY (IMAGERY) TESTING SESSIONS

2:00 PM	Set-up for plasma (IV insert) measures; physiological Setup - HR, BP, Finger Temp, SCL.

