The Substance Use Calendar was developed by Miller and DelBoca (1994) and is based on the Time-Line Follow-Back Method (TLFB) (Sobell, Maisto et al. 1980). The SUC uses a calendar prompt and a number of other memory aids (e.g., holiday, payday, and other personally relevant dates) to facilitate accurate recall of daily drug use during the targeted period. It has demonstrated adequate levels of reliability and validity when administered as an in-person interview, over the telephone, and when administered via computer (e.g. Carey, 1997; Sobell, Brown, Leo, & Sobell, 1996; Sobell, Sobell, Leo & Cancilla, 1988). Its reliability and validity in drug abusing samples has also been established (Fals-Stewart, et al., 2000). In the current study we will use to obtain self-report of day to day use of alcohol, and other drugs, for the 90 days prior to treatment and weekly during treatment.

The Smoking History Questionnaire will be given to collect information on current and past smoking habits. The questionnaire also questions the subject's number of past quit attempts, their perception of health risks, and perceived barriers to quitting.

Fagerstrom Test for Nicotine Dependence (FTND: Fagerstrom, 1978) is a 6-item questionnaire for assessing tobacco dependence, which evaluates, among other factors, depth of inhalation, time from awakening to day's first cigarette, and difficulty in smoking cessation.

The Alcohol Use Disorders Identification Test (AUDIT) (Bohn et al., 1995) is a 10-item screening tool developed by the World Health Organization (WHO) to assess alcohol consumption, drinking behaviors, and alcohol-related problems.

Alcohol Dependence Scale (ADS) is a 25 item to measure severity of alcohol dependence.

Abstinence Measures:

Clinical Institute Withdrawal Assessment (CIWA) is a 13 item scale that measures alcohol withdrawal signs and symptoms. The assessment will be administered weekly and at followup interviews.

Cocaine Selective Severity Assessment (CSSA) is an 18-item scale that measures the cocaine withdrawal signs and symptoms within the past 24 hours. The CSSA will be used weekly and at the follow-up interview.

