Hypothesis 3a: AUD patients on PREG doses versus those on PLA will dose dependently show (a) Primary: higher alcohol abstinence days, lower mean heavy drinking days and lower amounts of alcohol used in the 8-week treatment period, and (b) secondary: lower alcohol craving, anxiety and negative mood symptoms.

Specific Aim #3b: To assess whether PREG-stimulated ALLO levels mediate its effects on primary alcohol use outcomes and on secondary clinical outcomes during the 8-week treatment phase. Hypothesis 3b: Compared to PLA, higher ALLO levels in the PREG dose groups will dose dependently mediate primary and secondary alcohol use outcomes predicted in the above Hypothesis 3a with the PREG 500mg group showing better primary and secondary outcomes than the PREG 300mg group who will be better than outcomes in the PLA group.

Exploratory Aim: To explore whether pre-treatment patient characteristics (gender, family history of alcoholism (FH), trauma history and co-morbid drug use) influence PREGpotentiated ALLO levels and primary and secondary alcohol use outcomes.

Exploratory analyses using mixed effects models and MRMs will be conducted to assess if pretreatment characteristics and laboratory responses (average or AUC) are predictive of primary alcohol use outcomes.

SECTION VI: RESEARCH INVOLVING DRUGS, BIOLOGICS, RADIOTRACERS, PLACEBOS AND DEVICES

If this section (or one of its parts, A or B) is not applicable, state N/A and delete the rest of the section.

A. DRUGS, BIOLOGICS and RADIOTRACERS

1. Identification of Drug, Biologic or Radiotracer: What is (are) the **name(s)** of the drug(s) biologic(s) or radiotracer(s) being used? Identify whether FDA approval has been granted and for what indication(s).

Pregnenolone is a naturally occurring steroid, which is available as a dietary supplement in health stores. **Under the Dietary Supplement Health and Education Act of 1994 (DSHEA), a dietary supplement is not considered a drug if the intended use is only to affect any function of the body.** In this pilot study, we are looking at pregnenolone's effect on function in the body and we will be collecting preliminary alcohol and drug use outcome data.

All protocols which utilize a drug, biologic or radiotracer **not** approved by, but regulated by, the FDA, or a radiotracer regulated by the RDRC, must provide the following information:

- a. What is the Investigational New Drug (IND) **number** assigned by the FDA?
- b. Who holds the IND?

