If a subject decides to not continue with the treatment phase, twice-weekly follow-up appointments for one week will be scheduled after the laboratory sessions are complete. They will receive \$25 for each visit. Therefore, if subjects only complete the laboratory phase with the follow up visits and smartphone monitoring, the maximum total payment will be \$490.

3. Costs for Participation (Economic Considerations): Clearly describe the subject's costs associated with participation in the research, and the interventions or procedures of the study that will be provided at no cost to subjects.

There will be no costs charged to subjects who participate in this study. All evaluations including interviews, physical exams, diagnostic tests will be provided at no cost to the subjects.

4. **In Case of Injury:** This section is required for any research involving more than minimal risk.

- a. Will medical treatment be available if research-related injury occurs?
- b. Where and from whom may treatment be obtained?
- c. Are there any limits to the treatment being provided?
- d. Who will pay for this treatment?
- e. How will the medical treatment be accessed by subjects?

While medical therapy will be offered for any physical injuries sustained as a consequence of participation in this research, the subject and their insurance carrier will be responsible for the cost of such treatment. Financial compensation for injury is not available.

REFERENCES

Beck, A., C. Ward, et al., (1961). "An inventory for measuring depression." *Archives of General Psychiatry* 4: 461-471.

Bradley, B. P., Phillips, G., Green, L., Gossop, M., (1989). "Circumstances surrounding the initial lapse to opiate use following detoxification." *Br. J. Psychiatry.* 154, 354-359.

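### Randomized participants who opt out after the week-2 laboratory sessions have no scheduled drinking data for roughly 35 to 39 of the 56 outcome days

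*Combined protocol and SAP*

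**What the plan says.** **Order of events.** Section V, item 3 (Study Design and Overview) states that "participants will be randomly assigned to 2 doses of PREG (300/500 mg/day) vs placebo (PLA) treatment (N=30/group) over 8 weeks". Under General Procedures, once intake is complete, "s/he will be randomized to 300mg PREG, 500mg PREG, or PLA and exposed to three laboratory sessions as close together as possible". The laboratory text gives the timing: "In week 2 of the study PREG/PLA administration and hence DAY 1, 2 and 3 of the laboratory portion of the study". A session goes ahead only at zero breath alcohol, "otherwise the session will be rescheduled". Randomization and dosing therefore precede the laboratory sessions.

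**Outcome window.** Hypothesis 3a (Section V, item 12) names abstinent days, heavy drinking days and "lower amounts of alcohol used in the 8-week treatment period" as primary. The same item gives weekly urine screens and the Substance Use Calendar as the sources. The Calendar's own description schedules it for the 90 days before treatment and then weekly while treatment lasts.

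**People who opt out.** Section X, item 2 treats the period after the laboratory sessions as something a participant may decline. For those who decline, "twice-weekly follow-up appointments for one week will be scheduled after the laboratory sessions are complete", at 25 dollars a visit. The maximum payment for laboratory phase, these visits and smartphone monitoring is 490 dollars.

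**Related text.** The follow-up procedures in Section V, item 3 include "arranging for home visits and telephone interviews when subjects fail to keep appointments" and incentive payments for follow-up evaluations, all to be used in this study. The ASI is planned before treatment, at week 8 and 30 days after treatment. Neither place says how it applies to someone who stops after the laboratory sessions.

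**The concern.** A person who opts out after the laboratory sessions has been randomized and has taken study medication, and so belongs in the comparison of arms. The only visit schedule written for that person stops well before the primary window closes. Opting out could plausibly depend on how much the person is drinking, how the medication is tolerated, or which arm they are in.

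If it does, the drinking comparison is exposed whichever analysis is used. Dropping these people loses the protection of randomization. Keeping them with partial data relies on assumptions that the data cannot check. Section V, item 12 says that the results will supply effect sizes for a larger trial, so a distortion here would carry into its planning.

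**Working it through.** **Inputs**

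- Outcome window: 8 weeks = 56 days (Section V, item 3; Hypothesis 3a).
- Laboratory sessions: three separate days in week 2, that is days 8 to 14. Held on consecutive days they finish on day 10 at the earliest, and on day 14 at the latest if kept within the week. These day numbers are derived, not stated.
- Follow-up after opting out: 7 days (Section X, item 2).
- Payment amounts: Section X, item 2.

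**Step 1. Reproduce the plan's own figure, 490 dollars**

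- Intake 25 + training 25 + sessions 3 × 100 + bonus 50 = 400.
- Follow-up visits: 2 × 25 = 50.
- Smartphone monitoring per full week: 7 × 2 + 6 = 20.
- 400 + 50 + 20k = 490 gives k = 2 weeks exactly. Three weeks would give 510 and eight would give 610.
- The completer total also reproduces: 400 + 160 + 200 + 3 × 25 + 25 = 860.

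The maximum for someone who stops after the laboratory phase therefore contains two visits and two diary weeks. If the diary starts on day 1 (the start day is not stated), paid diary data end near day 14, or 14/56 = 25% of the window.

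**Step 2. How much of the window has scheduled visits**

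Last visit day = last laboratory day + 7.

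| Sessions end | Visits end | Observed share | Days with none scheduled |
|---|---|---|---|
| Day 10 | Day 17 | 17/56 = 30.4% | 39 (69.6%) |
| Day 14 | Day 21 | 21/56 = 37.5% | 35 (62.5%) |

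Each day by which a rescheduled session runs past day 14 adds one observed day.

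**Step 3. Share of all planned person-days affected**

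Share = p × 35/56, where p is the proportion opting out and visits end on day 21. The protocol gives no p for this trial. Its only related figure is 92% completion in past stress studies (8% loss); the other values are assumptions.

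- p = 8%: 5.0%
- p = 20%: 12.5%
- p = 30%: 18.8%
- p = 40%: 25.0%

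**Step 4. What the gap does under each analysis**

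- *Raw counts of days.* The shortfall per leaver is rate × 35. At an assumed 40% heavy days, 21 × 0.4 = 8.4 are recorded against 56 × 0.4 = 22.4, which is 14 too few (7 to 21 at 20% to 60%). Total amount is understated too, and both errors look like benefit. Abstinent days are understated in the same way, which looks like harm.
- *Proportions of observed days only.* Suppose 60% of the first 21 days are abstinent and 40% of the remaining 35. The observed value is 60%; the 8-week value is (21 × 0.6 + 35 × 0.4)/56 = 47.5%. If the rate does not change over time there is no error. A denominator alone is therefore not enough.
- *Continuers only.* The randomized comparison is lost.
- *Mixed model or Cox model.* Validity rests on data missing at random, or on censoring unrelated to relapse risk.

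**The case against.** The strongest reply is that the one-week rule sits in a payments section. It schedules and pays for two visits; it does not say that outcome collection ends. Elsewhere the protocol promises tracing, telephone interviews and paid follow-up evaluations, and plans ASI interviews at week 8 and 30 days after treatment. Nor does the lack of a payment line prove that no interview takes place: the 860-dollar completer total has no line for the 30-day interview either. This stands in part. A reader might infer that these participants' later drinking will never be collected, and the protocol does not say so. But tracing is triggered by missed appointments, and after the one-week visits a leaver has none scheduled to miss. The ASI is a severity interview, not the daily record on which the primary outcome rests.

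Four further readings are tempting and go beyond the text:

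- *Everyone who leaves after randomization is cut off at day 21.* The rule covers only those who opt out after the laboratory phase. For other leavers the protocol gives no rule, and day 21 is the upper end of a derived range.
- *Payments to leavers cover only the extra week.* The 490 dollars also contains 40 for smartphone monitoring.
- *The arm with more leavers looks better.* With raw counts that holds for heavy days and amount, and reverses for abstinent days.
- *The plan compares truncated counts or continuers only.* It states neither. Section V, item 12 names mixed models for every specific aim, non-parametric tests for alcohol use and Cox models for relapse, with no analysis set, censoring rule or missing-data rule specific to drinking. Its remark that mixed models accommodate missing data comes in the account of the laboratory component.

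It is also fair to say that this is a preliminary and largely descriptive study. With 30 per arm, the standard error of a difference is about √(2/30) = 0.26 SD, so random error may exceed this bias. That limits the urgency. It does not justify leaving out data that are cheap to collect.

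**Conclusion.** The concern holds in this form: for randomized participants who opt out after the laboratory sessions, roughly 35 to 39 of the 56 days in the primary drinking window have no planned collection. This assumes sessions kept within week 2; rescheduling narrows the gap. The tracing and ASI text neither fills the gap nor rules out later collection, so it needs to be reconciled with Section X, item 2.

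Whether bias follows depends on opting out being related to drinking or arm, which is plausible but not shown. Its size cannot be stated. With raw counts at the assumed 40% heavy days, leaving rates of 25% and 10% would give a spurious difference of 0.15 × 14 = 2.1 heavy days, while 4 leavers against 2 out of 30 per arm would give (2/30) × 14 = 0.9. Both results come from assumed rates and an analysis that the protocol does not specify, so neither should be quoted as an estimate. The change is worth making because it is cheap and protects the primary comparison.

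**What to change.** - State in Section V, item 3 that the Substance Use Calendar is completed through day 56 for everyone randomized, whether or not they continue treatment, unless they withdraw consent to further contact. For leavers this can be done by telephone, weekly or as one catch-up interview at week 8.
- Reconcile Section X, item 2 with the tracing procedures and the ASI schedule. Say what week 8 and the post-treatment interview mean for someone who stopped early, and apply the same collection rule to people who leave at other times.
- In Section V, item 12, analyse all randomized participants on proportion of abstinent days, proportion of heavy drinking days and mean amount per day. Add a censoring rule for the relapse analysis and a missing-data rule for days that remain unobserved.

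The means are already in the protocol. It describes the Calendar as having "adequate levels of reliability and validity when administered as an in-person interview, over the telephone", and a catch-up interview spanning 35 to 39 days is shorter than the 90-day recall used at baseline.

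The cost is one to five short calls (35/7 = 5 if weekly) and a small payment per leaver. At the historical 8% loss that is 90 × 0.08 = 7.2, about 7 people; at an assumed 20% it is 18. Telephone reports also lack urine or breath confirmation, which should be acknowledged when results are reported.
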